6.7 Sample Collections

Site personnel will collect blood samples at the visits specified in Section 6.1. These samples will be processed at the site and shipped same day to a central laboratory, as specified in the laboratory manual. [REDACTED]

[REDACTED]

[REDACTED]

[REDACTED]

[REDACTED]

7 Statistical Considerations

This section briefly describes statistical and analytical methods to be used for the study. A statistical analysis plan (SAP) will provide details of the statistical methods and definitions for the analysis of efficacy and safety data. To preserve the integrity of the statistical analysis and study conclusions, the SAP will be finalized before database lock.

7.1 Estimands

[REDACTED]

7.2 Sample Size Calculations

Fifteen patients will be randomly assigned to each of four treatment arms (placebo, ABP-450 low dose, ABP-450 medium dose, and ABP-450 high dose) using a 1:1:1:1 ratio and therefore requiring a total of 60 patients. [REDACTED]

[REDACTED]

[REDACTED]

[REDACTED]

[REDACTED] [REDACTED]

[REDACTED]

[REDACTED]

[REDACTED]

[REDACTED]

7.3 Analysis Sets

The following analysis sets will be used in the statistical analyses.

Full Analysis Set (FAS): The FAS will consist of all patients who received investigational study drug. All analyses using the FAS will group patients according to randomized treatment.

Modified Full Analysis Set (mFAS): The mFAS will consist of all patients in the FAS, but will exclude data points after patients have a significant change to their “stable” background medication, receive a dose outside of the set dose amounts, or receive further treatment. All analyses using the mFAS will group patients according to randomized treatment.

Per-Protocol Analysis Set (PPS): The PPS will consist of all patients in the FAS who received placebo or ABP-450 (according to the set dose amount), but will exclude all patients who

discontinued the study prior to Week 4 or had significant protocol violations affecting evaluation of the primary endpoint. All analyses using the PPS will group patients according to actual treatment received.

Safety Analysis Set: The Safety Analysis Set will consist of all patients who received any investigational study drug. All analyses using the Safety Analysis Set will group patients according to treatment actually received.

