5.8 Prior and Concomitant Therapy

Use of all concomitant medications will be recorded in the patient's eCRF. The minimum requirement is that drug name, dose, and dates of administration are to be recorded. This will include all prescription drugs, herbal products, vitamins, minerals, and over-the-counter medications. Any changes in concomitant medications also will be recorded in the patient's eCRF.

Any concomitant medication deemed necessary for the welfare of the patient during the study may be given at the discretion of the investigator. However, it is the responsibility of the investigator to ensure that details regarding the medication are recorded in full in the eCRF.

6 Study Assessments and Procedures

Before performing any study procedures, all potential patients will sign an informed consent form (ICF). Patients will have the opportunity to have any questions answered before signing the ICF. The investigator must address all questions raised by the patient. The investigator or designee will also sign the ICF.

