3.4. Dose Adjustment/Modifications

Investigational study drug dose modifications are not allowed.

4. General Statistical Considerations

The statistical principles applied in the design and planned analyses of this study are consistent with International Council for Harmonisation (ICH) E9 guidelines (ICH 1998).

A thick black horizontal bar, likely a redacted section of text.

Data summaries will be presented by treatment group unless otherwise specified. All efficacy analyses will be based upon the Full Analysis Set (mFAS, Section [REDACTED]
[REDACTED]), and all safety as well as demographic and baseline characteristic analyses will be based upon the Safety Analysis Set (Section 4.3.5). Additional analyses will be performed on selected populations as specified in the sections below.

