4.3.3. Modified Full Analysis Set (mFAS)

The mFAS will consist of all patients in the FAS, but will exclude patients who have a

[REDACTED]

[REDACTED] All analyses using the mFAS will group patients according to randomized treatment.

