9.1. Secondary Estimands

9.1.1. TWSTRS

Most studies leading to the approval of currently available botulinum neurotoxins have used the TWSTRS scale as the primary efficacy measure (Espay 2018, Fernandez 2013). The standard TWSTRS is a comprehensive scale that comprises three subsets to assess motor severity, pain, and disability (Comella 2016). The motor severity subscale consists of 10 items, with variable scaling and weighting. It also includes a disability subscale with 6 items and a pain scale with 3 items. The total score is the sum of each of the subscales.

Mean difference in change in the subscale scores of TWSTRS (disability, severity, and pain) from baseline to Week 4 for each of low, medium, and high doses of ABP-450 compared to placebo will also be analyzed [REDACTED]

Summary statistics for change from baseline of TWSTRS total score and subscale scores (disability, severity, and pain) every 4 weeks will be tabulated by treatment group and displayed in figures over time. [REDACTED]

Summary statistics for time to loss of $\geq 80\%$ of peak treatment effect for patients dosed on ABP-450 will be tabulated by treatment group. [REDACTED]

[REDACTED]

[REDACTED]

[REDACTED]
[REDACTED]
[REDACTED]
[REDACTED]
[REDACTED]
[REDACTED]
[REDACTED]

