9.2. Sensitivity Analyses

Sensitivity analysis will be performed for mean difference in TWSTRS total score from baseline to Week 4 for each low, medium, and high doses of ABP-450 compared to placebo, [REDACTED]
[REDACTED]

[REDACTED]. Similarly, mean difference in change in the subscale scores of TWSTRS (disability, severity, and pain) from baseline to Week 4 for each low, medium, and high doses of ABP-450 compared with placebo will be made, [REDACTED]

Additional sensitivity analyses will be performed for mean difference in TWSTRS total score (and subscale scores) from baseline to Week 4 for each low, medium, and high doses of ABP-450 compared to placebo for the FAS using the same analysis described in Section 9.1.1.

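### The 4-weekly TWSTRS curves to Week 20 could be biased by the mFAS exclusions: Protocol and SAP word the exclusion differently, and no readable method covers the removed scores at Weeks 8 to 20

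*Protocol*

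**What the plan says.** The mFAS of Protocol 7.3 starts from the FAS and "will exclude data points after patients have a significant change to their" usual dystonia drugs. Two other triggers are listed: dosing off the planned amounts, and being treated again. The patient stays in the set; scores after the event go.

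SAP 4.3.3 reads differently: "The mFAS will consist of all patients in the FAS, but will exclude patients who have a", followed by redacted text. As far as it can be read, the unit removed is the patient, not the score.

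SAP 4 states "All efficacy analyses will be based upon the Full Analysis Set (mFAS", mixing two labels. SAP 9 names the mFAS for inferential efficacy analyses, applies the PPS as well to TWSTRS analyses and summaries, and promises missing-data imputation section by section.

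SAP 9.1.1 plans "Summary statistics for change from baseline of TWSTRS total score and subscale scores (disability, severity, and pain) every 4 weeks will be tabulated" by arm and plotted over time. The text straight after is redacted. Protocol 7.5 describes general summaries as number of observations, mean, SD, median, range and missing data, so missing values are counted.

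The readable FAS sensitivity analysis in SAP 9.2 runs "from baseline to Week 4 for each low, medium, and high doses of ABP-450 compared to placebo for the FAS". Nothing readable extends it to later visits.

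On medication during the study, Protocol 5.8 says: "Any concomitant medication deemed necessary for the welfare of the patient during the study may be given at the discretion of the investigator".

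**The concern.** Patients whose effect never came or has worn off have the clearest reason to change dystonia medication or be treated again. If so, whether a late score is kept depends on how the patient was doing. The average of the kept scores then describes a selected group. With an active drug, more removals would be expected on placebo and the low dose, so the favourable shift would be largest there and the arms would move towards each other.

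The study is meant to help choose doses and follows patients for up to 20 weeks. Persistence of effect is one way doses can differ, and the 4-weekly curves are one of the two readable displays of it. The other, time to loss of at least 80% of peak effect, probably draws on the same late scores.

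The difference in mFAS wording matters separately. Under the Protocol rule, only events before Week 4 can touch the Week 4 secondary estimands. If whole patients are removed, an event at Week 12 also takes out that patient's Week 4 score.

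**Working it through.** **Plan's own figure.** 15 patients × 4 arms = 60, as stated in Protocol 7.2 and SAP 4.1. The documents give no late TWSTRS means, no SD and no event rate in readable text, so every other input below is an assumption.

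**Direction.** Let Y be a patient's TWSTRS change at a late visit (lower is better) and R = 1 if the score is kept. Then

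E[Y | R = 1] − E[Y] = Cov(Y, R) / Pr(R = 1).

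If patients doing badly are removed, Cov(Y, R) is negative and the kept mean is too low, that is, too favourable. If removal is unrelated to Y, the bias is zero. The bias in a between-arm gap is the difference between the two arms' terms.

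**Set-up A (200,000 simulated patients per arm).** Assumed true mean changes at Weeks 4/8/12/16/20:
- placebo −4, −3, −2, −1, −1
- 150 units −9, −8, −5, −3, −2
- 250 units −11, −10, −7, −4, −3
- 350 units −13, −12, −9, −6, −4

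Between-patient SD 8, within-patient SD 5. After each visit, a patient whose change is worse than −3 has event chance p before the next visit; later scores are dropped.

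| p | Placebo kept at Week 20 | Placebo mean, Week 20 (true −1.0) | 350 units minus placebo, Week 16 (true −5.0) | Week 20 (true −3.0) | Week 20, last score carried forward |
|---|---|---|---|---|---|
| 10% | 81% | −2.1 | −4.6 | −2.6 | −3.2 |
| 30% | 56% | −4.6 | −3.8 | −1.6 | −3.6 |
| 50% | 40% | −7.0 | −2.7 | −0.4 | −3.9 |

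The 350 minus 150 units difference at Week 20 (true −2.0) becomes −1.8, −1.3 and −0.7. With removal unrelated to the score (20% per interval), the observed-case Week 20 gap stays at −3.0.

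**Whole-patient exclusion, same inputs.** The Week 4 gap between 350 units and placebo falls from a true 9.0 to 8.5, 7.4 or 6.1 points at p = 10%, 30% or 50%.

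**Set-up B.** SD of change 10, within-patient correlation 0.6. True means at Weeks 16/20: placebo −1.0/−0.5, 150 units −2.5/−1.0, 250 units −4.0/−2.0, 350 units −5.5/−3.0. Events occur from Week 8 in patients with change above −2. Means at earlier visits were assumed to wane towards these values.
- True Week 20 gap, 350 units minus placebo: −3.0 − (−0.5) = −2.5, a gap of 2.5 points.
- Observed-case gap: about 2.4, 2.0 and 1.0 points at p = 10%, 25% and 50%. The 50% case removes about half of placebo by Week 20.
- Last score carried forward: about 2.8 to 3.4 points.

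A repeated-measures model fitted to the retained scores at 15 per arm recovered the true means within about 0.3 points. Removal there depended only on the last observed score, so it was missing at random by construction: the result shows that the model works under that assumption, not that the assumption holds in this trial.

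**Against sampling noise.** With SD 10 and 15 per arm, the standard error of a gap is 10 × √(2/15) ≈ 3.7 points before any removal. The largest set-up B bias, 2.5 − 1.0 = 1.5 points, is under half of that.

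**The case against.** A reader might infer that the late means will describe only patients still doing well and that the dose curves will be pulled together. The documents do not support that as fact.
- No passage gives an event rate or says that events follow poor response. Protocol 5.8 is a general concomitant-medication clause, and only a significant change to background medication triggers exclusion.
- SAP 9 promises imputation and the text after the 4-weekly sentence is redacted, so plain averaging cannot be confirmed. Carrying the last score forward reverses the direction.
- The curves are descriptive, and SAP 9 ties the mFAS firmly only to inferential analyses. The link from the curves to the mFAS runs through the mixed label in SAP 4.
- The efficacy objective is at Week 4, and no readable decision rule uses the late curves.

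All of this stands, and it makes the bias conditional. It does not remove the point. Protocol 7.5 suggests that summaries count missing values, and neither a method nor an FAS display for Weeks 8 to 20 is readable. The PPS summaries do not correct the mFAS curves: they drop other patients and group by treatment received.

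Dropping post-event scores does suit a hypothetical estimand, which the plan states for Week 4. But averaging whoever remains does not estimate what would have happened without the event, unless removal is unrelated to outcome.

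The redacted end of SAP 4.3.3 may bring it into line with the Protocol. As readable, the two differ.

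**Conclusion.** The concern holds conditionally. If medication changes or further treatment follow a poor or lost response, more often in some arms than others, and the remaining scores are averaged without a missing-data method, the late means are too favourable and late dose differences shrink. Under set-up B the loss from a 2.5-point Week 20 gap is about 0.1, 0.5 or 1.5 points at event chances of 10%, 25% or 50%: negligible if events are rare, more than half the gap in the extreme case. Compression of the curves cannot be claimed as certain, because the event rate, its link to response and any imputation rule are unknown.

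Under the Protocol wording the Week 4 estimands are exposed only to events before Week 4. Under the readable SAP wording, later events could reach them too; the Week 4 FAS sensitivity analysis would help to reveal this. The change is worth making because it is cheap and the late curves bear on dose choice.

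**What to change.** 1. Reconcile Protocol 7.3 and SAP 4.3.3 so that the mFAS keeps each patient's scores up to the event. Correct the mixed label in SAP 4, and name the analysis set and missing-data rule for the 4-weekly summaries and for time to loss of effect.
2. Unless the redacted text already does so, add to SAP 9.1.1 4-weekly arm means and differences from placebo from a repeated-measures model fitted to pre-event scores. Terms: arm by visit, baseline TWSTRS and randomisation stratum. Use unstructured covariance, with a pre-stated simpler structure if it does not converge, which is a real possibility at 15 per arm.
3. Keep the raw summary table beside it, and show the number removed and the reason by arm and visit.

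The cost is some SAP wording, one extra standard model and one table. The model relies on missing-at-random given earlier scores, which is weaker than what the raw means need (removal unrelated to the score) but still cannot be verified. If the redacted text already specifies such a model, step 2 needs only confirmation.

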7.4 Description of Subgroups to be Analyzed

No subgroup analyses are planned.

7.5 Statistical Analysis Methodology

Variables will generally be summarized using number of observations, mean, SD, median, minimum, maximum, and missing data (for continuous variables) and using frequencies, percentages, and missing data (for categorical variables). Data will be listed in data listings.

Details of the statistical analyses, methods, and data conventions are described in the SAP.

7.5.1 Analysis of Primary Estimand

The proportion of patients with treatment-related SAEs up to Week 20 and the end of a single treatment cycle will be summarized separately for ABP-450 (all doses together and separately) and placebo.

Treatment-related SAEs will be counted if they start prior to administering any further treatment irrespective of change to background treatment or low doses that were below the set low-dose amount (ie, below 150 units) or high doses that were above the set high-dose amount (ie, above 350 units).

7.5.2 Analysis of Secondary Estimands

The analysis of the first secondary efficacy estimand is based on the comparison of least square means

7.5.3 Safety Analyses

The incidence of treatment-emergent AEs for the Safety Analysis Set will be summarized by treatment group. Adverse events will be coded using MedDRA to classify events under primary system organ class and preferred term. [REDACTED]

Term	Percentage
GMOs	85%
Organic	82%
Natural	78%
Artificial	65%
Organic	80%
Natural	75%
Artificial	60%
Organic	88%
Natural	80%
Artificial	70%

7.5.4 Other Analyses

Summary statistical analyses will be provided by treatment group for demographics, background characteristics, medical history, and physical examination results.

7.5.5 Interim Analyses

No interim analyses are planned.

1

8 Data Quality Assurance

The sponsor or its designee will perform the quality assurance and quality control activities of this study, including regular monitoring visits to study sites and meeting with site personnel. However, the investigator generating the data will be responsible for the accuracy, completeness, and reliability of the study data presented to the sponsor.

8.1 Data Management

As part of the responsibilities assumed by participating in the study, the investigator agrees to maintain adequate case histories for the patients treated as part of the research under this protocol. The investigator agrees to maintain accurate eCRFs and source documentation as part of the case histories. These source documents may include laboratory reports and [REDACTED]

All eCRF information is to be filled in. If an item is not available or is not applicable, this fact should be indicated. Blank spaces should not be present unless otherwise directed. A correction to source documentation should be made by striking through the incorrect entry with a single line, and the corrected information should be entered adjacent to the deleted item. The correction must be initialed and dated by the person making the correction.

Investigative site personnel will enter patient data into an electronic data capture system. The analysis data sets will be a combination of these data and data from other sources (eg, laboratory data).

Clinical data management will be performed in accordance with applicable Aeon Biopharma standards and data cleaning procedures to ensure the integrity of the data, eg, removing errors and inconsistencies in the data. Adverse event terms will be coded using MedDRA, an internal validated medical dictionary, and concomitant medications will be coded using the World Health Organization Drug Dictionary.

[REDACTED]
[REDACTED]
[REDACTED]
[REDACTED]
[REDACTED]
[REDACTED]

9 Ethics

9.1 Independent Ethics Committee or Institutional Review Board

Federal regulations and the ICH guidelines require that approval be obtained from an IRB/IEC before participation of human patients in research studies. Before study onset, the protocol, informed consent, advertisements to be used for the recruitment of study patients, and any other written information regarding this study to be provided to the patient must be approved by the IRB/IEC. Documentation of all IRB/IEC approvals and of the IRB/IEC compliance with ICH harmonised tripartite guideline E6(R2): Good Clinical Practice (GCP) will be maintained by the site and will be available for review by the sponsor or its designee.

All IRB/IEC approvals should be signed by the IRB/IEC chairman or designee and must identify the IRB/IEC name and address, the clinical protocol by title or protocol number or both, and the date of approval or the date a favorable opinion was granted.

The investigator is responsible for providing written summaries of the progress and status of the study at intervals not exceeding 1 year or otherwise specified by the IRB/IEC. The investigator must promptly supply the sponsor or its designee, the IRB/IEC, and, where applicable, the institution with written reports on any changes significantly affecting the conduct of the study or increasing the risk to patients.

9.2 Ethical Conduct of the Study

The study will be performed in accordance with the ethical principles that have their origin in the Declaration of Helsinki, ICH GCP, the protocol, and all applicable regulations.

9.3 Patient Information and Consent

A written informed consent in compliance with United States Title 21 Code of Federal Regulations (CFR) Part 50 shall be obtained from each patient before entering the study or performing any study procedure. An informed consent template may be provided by the sponsor to investigative sites. If any institution-specific modifications to study-related procedures are proposed or made by the site, the consent should be reviewed by the sponsor or its designee or both before IRB/IEC submission. Once reviewed, the consent will be submitted by the investigator to his or her IRB/IEC for review and approval before the start of the study. If the ICF is revised during the course of the study, all active participating patients must sign the revised form.

Before recruitment and enrollment, each prospective patient will be given a full explanation of the study and be allowed to read the approved ICF. Once the investigator is assured that

the patient understands the implications of participating in the study, the patient will be asked to give consent to participate in the study by signing the ICF.

The investigator shall retain the signed original ICF(s) and give a copy of the signed original form to the patient.

10 Investigator's Obligations

The following administrative items are meant to guide the investigator in the conduct of the study but may be subject to change based on industry and government standard operating procedures, working practice documents, or guidelines. Administrative changes will be reported to the IRB/IEC but will not result in protocol amendments.

10.1 Confidentiality

All laboratory specimens, evaluation forms, reports, and other records will be identified in a manner designed to maintain patient confidentiality. All records will be kept in a secure storage area with limited access. Clinical information will not be released without the written permission of the patient, except as necessary for monitoring and auditing by the sponsor, its designee, the FDA, or the IRB/IEC.

The investigator and all employees and coworkers involved with this study may not disclose or use for any purpose other than performance of the study any data, record, or other unpublished, confidential information disclosed to those individuals for the purpose of the study. Prior written agreement from the sponsor or its designee must be obtained for the disclosure of any said confidential information to other parties.

10.2 Financial Disclosure and Obligations

Investigators are required to provide financial disclosure information to allow the sponsor to submit the complete and accurate certification or disclosure statements required under 21 CFR 54. In addition, the investigator must provide to the sponsor a commitment to promptly update this information if any relevant changes occur during the course of the investigation and for 1 year following the completion of the study.

Neither the sponsor nor █ is financially responsible for further testing or treatment of any medical condition that may be detected during the Screening process. In addition, in the absence of specific arrangements, neither the sponsor nor █ is financially responsible for further treatment of the patient's disease.

